The national public health opioid crisis has disproportionately burdened rural white populations, and disproportionately burdened American Indian populations. Therefore, the Cherokee Nation (CN) and Emory University public health scientists have designed an opioid prevention trial to be conducted in at-risk rural communities in the CN (in northeast Oklahoma) with white and American Indian adolescents and young adults. Our goal is to implement and evaluate a theory-based, integrated multi-level community intervention designed to prevent the onset and escalation of opioid and other drug misuse. We propose a community randomized trial building directly on the success of our most recent previous trial, which demonstrated that our intervention effectively reduced alcohol and other drug use among American Indian and other youth living within the CN. Two distinct intervention approaches—community organizing as implemented in our established CMCA intervention protocol, and universal school-based brief intervention and referral as implemented in our established CONNECT intervention protocol—will be expanded and integrated to further enhance effects in preventing and reducing opioid misuse. The CMCA and CONNECT interventions were originally designed to target adolescent alcohol use, but nevertheless showed significant beneficial effects also on use of other drugs, including prescription drug misuse. The proposed study will: (1) further improve the design of the interventions with increased focus on opioids, (2) test the expanded, integrated versions in a community randomized trial, and (3) design and test new systems for sustained implementation within existing structures of the Cherokee Nation. Building upon the extant prevention science evidence, our study will respond to a gap in evidence concerning opioid misuse prevention among at-risk adolescents transitioning to young adulthood among American Indian and other rural youth. Our previous trial, conducted in partnership with the Cherokee Nation, ended with youth attaining age 18; the proposed new trial will additionally advance the science regarding strategies to engage young adults as they transition beyond high school.

II. Methods and Study Population

[figure not shown]
Sample

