The evaluation of the prevention programs will be accomplished through self-report surveys of a cohort of high school students followed over three years, from grade 10 (ages 15-17) to the year following high school graduation (ages 18-20). A pilot survey will be administered in the study schools using all approved protocols in grade 9. The main outcome analysis will include baseline (fall of 10th grade) through spring of 12th grade surveys. A secondary outcome analysis will include the six-month follow-up survey conducted six months post on-time high school graduation.

Recruitment Procedures

All 10th grade students enrolled in the participating study high schools will be eligible to participate in the study. As a universal preventive intervention, and given the need for a community-wide representative sample, there are no exclusionary criteria. Beginning in 10th grade, a cohort of high school students will be asked to participate in a brief, 20-30-minute, web-based survey on health behaviors two times per year. The survey will be administered using REDCap or Qualtrics on cellular-connected project tablets and implemented during homeroom, a class period, lunch period, or at

another time convenient to each school and participant. All data will be encrypted as soon as it is entered and transmitted to a central server at Emory University. No school personnel will be involved in any survey administration tasks, avoiding any potential risks and biases that could accrue from the involvement of school personnel in survey administration.

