Throughout the study, age ranges of the students will be from 15 to 20. Students will complete a short (20-30-minute) survey each semester within their homeroom, selected class period, or lunch period or on their own time through electronic survey distribution and once again approximately six months following graduation to monitor influences and outcomes. When in-school survey administration is not feasible students will be asked to participate in a private location through an electronic survey link. On average, each student will provide approximately seven data points throughout the project, so we can analyze trends over time in the onset and escalation of risk and protective factors and drug use outcomes.

We will analyze the effects of the CMCA and CONNECT interventions on proximal outcomes (e.g., perceived availability of drugs, social normative beliefs, social support, self-efficacy, and normative estimates of peer drug use) and on distal outcomes of opioid and other drug use (e.g., prescription opioids without a doctor telling you to take them, marijuana use, alcohol use). The trial consists of "doubly repeated" measures--repeated measures nested within each student, plus students are nested within schools. Any statistical analysis that ignores lack of independence due to nesting will be subject to inflated type-1 errors. To account for both the clustering effect of students nested within schools and repeated measures nested within student, intervention effects on proximal and drug use outcomes will be estimated with generalized linear mixed models.

As part of our strategy to follow students into the first year after their expected graduation, we will employ extensive tracking procedures to maintain a high response rate across study waves. There may still exist students who miss survey administrations or who are lost to follow-up. As in our previous Cherokee Nation prevention trial, we will use multiple imputation to account for non-response over time and potential attrition. All available outcomes data will be used to impute missing outcome data from those with missing survey waves.

VI. Dissemination

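### Does section V need a named primary drug-use outcome and a multiplicity rule before its results can be trusted?

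*Combined protocol and SAP*

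**What the plan says.** Section V names three drug-use outcomes as examples: "distal outcomes of opioid and other drug use (e.g., prescription opioids without a doctor telling you to take them, marijuana use, alcohol use". It also gives five example proximal outcomes. The method is the same for all of them: "intervention effects on proximal and drug use outcomes will be estimated with generalized linear mixed models". The section's one remark on type I error concerns clustering: "Any statistical analysis that ignores lack of independence due to nesting will be subject to inflated type-1 errors". It states no significance level, sidedness, testing order or adjustment for several outcomes.

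Section II, just before Recruitment Procedures, does separate main from secondary analysis, but by survey wave. "The main outcome analysis will include baseline (fall of 10th grade) through spring of 12th grade surveys", whereas "A secondary outcome analysis will include the six-month follow-up survey conducted six months post on-time high school graduation".

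The opening section describes the purpose in two ways. The investigators "have designed an opioid prevention trial to be conducted in at-risk rural communities", and the intervention is "designed to prevent the onset and escalation of opioid and other drug misuse". Of the earlier versions of the two programmes, aimed at alcohol, it says they "nevertheless showed significant beneficial effects also on use of other drugs, including prescription drug misuse". The waiver argument under Informed Consent (third criterion) treats substance use in general as the main dependent variable, without choosing a substance. Section VI (Dissemination) commits the sponsor to registering the trial and to papers on design and on outcomes.

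**The concern.** Three drug-use outcomes go to the same model with none marked as decisive, and the list is open because it is given as examples. A reader of section V alone cannot say whether a significant marijuana or alcohol result beside a null opioid result would be reported as success. The opening section already cites effects of the earlier programmes on drugs they did not target as a benefit, so that reading is not far-fetched.

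If any of the three could carry the claim, the false-positive rate of the main conclusion would exceed that of one test. The clustering remark does not help, because a mixed model protects the level of each test and not of the set.

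**Working it through.** The plan gives no significance level, power or familywise error figure, so there is nothing of its own to reproduce. The size of the concern is computed from stated assumptions.

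**Inputs**
- Number of drug-use outcomes: 3 (section V, as examples).
- Arms: 2, hence one contrast per outcome (section II, Sample).
- Level: two-sided 5% per outcome, i.e. 2.5% in the favourable direction (assumed).
- Common correlation r between test statistics: 0 to 0.9 (assumed).
- Success rule: any one outcome significant in the favourable direction (assumed; not stated anywhere in the supplied text).
- Each mixed-model test holds its nominal level (assumed).

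**False-positive rate, any of three**

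For r = 0: 1 − 0.975³ = 1 − 0.9269 = 0.0731.

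For r > 0: 1 − ∫ φ(x) [Φ((1.96 − √r·x)/√(1 − r))]³ dx.

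| r | any of three | opioid outcome alone |
|---|---|---|
| 0 | 7.3% | 2.5% |
| 0.3 | 6.8% | 2.5% |
| 0.5 | 6.3% | 2.5% |
| 0.7 | 5.5% | 2.5% |
| 0.8 | 4.9% | 2.5% |
| 0.9 | 4.2% | 2.5% |

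The whole excess comes from the assumed success rule. Adding the five proximal outcomes on equal terms would give 18.3% (r = 0) to 6.0% (r = 0.9). That scenario has no support: section V itself separates proximal from distal outcomes, and nothing suggests that a change in, say, social support could carry the efficacy claim.

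**Cost of a formal rule**

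Assume 80% power for a responding outcome at two-sided 5%, a shift of 1.96 + 0.84 = 2.80.

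- *Holm, one outcome responds.* The first step uses 0.05/3, critical value 2.394. Power = Φ(2.80 − 2.394) = Φ(0.41) = 65.8%. With 14 to 22 degrees of freedom (16 to 24 schools, less 2) it is 62.1% to 63.5%.
- *Holm, two or three respond (simulation, 1,000,000 draws).* Power for one given responding outcome is 68–70% with two responding and 72–75% with three. Power to claim at least one is 72–88% and 75.5–96% (r = 0.9 to 0). The corresponding unadjusted figures are 85–96% and 87–99%.
- *Fixed order, opioid misuse first.* The opioid outcome keeps 80% power. If opioids do not respond, a real effect placed second can be claimed only when the first test is falsely significant. At r = 0 that is 0.05 × 0.80 = 4.0% with a two-sided gate, or 0.025 × 0.80 = 2.0% with a favourable-only gate. At r = 0.9 it is about 2.5% for both gates.

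**Which reading the text supports**

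The opening section calls this an opioid trial, says the programmes are being expanded to strengthen their effect on opioid misuse, makes a greater opioid emphasis the first aim, and places the evidence gap in opioid prevention. Section V lists opioids first. Against this stand the wider goal, which adds other drugs, and the general reference to substance use in the waiver argument. The balance is towards opioids, though not settled. The sentence on the earlier programmes reports history and sets no success rule for this trial.

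**The case for a change.** The strongest case for acting is that the omission is real and cheap to mend. Nothing in the supplied text identifies the deciding outcome. Section V does not point to a registry entry or a design paper. The sponsor's own account of the earlier trial shows a readiness to credit effects on several substances. A few words in section V would remove the doubt, with no new data.

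The omission stands, and so does the 4–7% range under its assumptions. What does not follow is that the plan is wrong. The range needs a level, a correlation and a success rule that the supplied text does not contain. If a primary outcome is registered, as section VI promises the trial will be, the point reduces to repeating that outcome in section V. If none is registered, the sponsor must choose between two defensible rules with opposite weaknesses: one nearly gives up a real marijuana or alcohol effect when opioids do not respond, and the other lowers power for a lone opioid effect from 80% to about 66%. That is a trade-off for the investigators, not an error with one correct repair. The registry record, the attached survey and some removed pages were not available, so the gap may be smaller than it looks.

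**Conclusion.** No change is called for. As supplied, section V does not say which drug-use outcome is primary or at what level it is tested, but this is missing detail and no stated rule yields a wrong result. At an assumed two-sided 5%, the chance of a falsely favourable conclusion is 2.5% if opioid misuse alone decides, the reading the opening section favours. It is about 4–7% (r = 0.9 to 0) only if any one of the three named outcomes may be claimed as success, which the supplied text does not say. Analysts can fill the gap sensibly from the registered outcome and the trial's stated opioid purpose, reporting the other substances as secondary. A formal rule across all three would cost power in ways that reasonable statisticians would weigh differently.

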A series of mailings (1 introduction postcard, 1 informed consent letter, 1 reminder postcard) will be sent to parents/guardians of all 10th grade students in the participating schools. The letter sent to parents includes the information required for informed consent set forth in 45 CFR 46.116. Parents can refuse participation for their child by calling [name] (contact information provided) using a toll-free number or by mailing a pre-addressed postage-paid postcard. Students will provide assent to participate. Assent forms will be read aloud prior to the administration of each survey. Follow-up calls or in-person meetings will be made to parents who request more information or are otherwise unreachable. The consent and assent forms include a statement indicating that they may decline participation without any repercussions and may terminate participation in the surveys at any time. The form also states that participation in this study will in no way influence their school standing, grades, or evaluations, and for parents, that it will not affect their status in the school, with the Cherokee Nation, or any other standings. Methods to ensure confidentiality will also be explained. Any questions youth have will be answered. Only those who have been read assent forms and whose parents have not refused consent via the postcard or phone will be included in the study. Copies of the consent mailings and assent form are included in this submission.

Waiver of Written Parental Consent

In our previous prevention trial in the Cherokee Nation, which included the community (CMCA) and screening and brief intervention (CONNECT) prevention interventions and a youth survey as proposed here, we were granted a waiver of written parental consent. We understand in order to justify a waiver of written parental consent; the following four criteria must be met [45 CFR 46.116 (d)]:

1. The research involves no more than minimal risk to the subjects;
2. The waiver or alteration will not adversely affect the rights and welfare of the subjects;
3. The research could not practicably be carried out without the waiver or alteration; and
4. Whenever appropriate, the subjects will be provided with additional pertinent information after participation.

We believe our procedures and study protocol fulfill these four criteria and the criteria outline in 45 CFR 46.408. This has been confirmed by continued prior approval of these procedures by the University of Florida Institutional Review Board and Cherokee Nation Institutional Review Board in 2011 and Emory University's Institutional Review Board in 2015. Our justification to waive the requirement of written parental consent is as follows:

(1) The research involves no more than minimal risk to the subjects.

Risks posed by the survey are no more than minimal. The questions have been used with thousands of children since 1975, and are the same as those used in federal government surveys, such as those supported by CDC and NIDA. The survey does not probe psychologically (such as with the use of clinical psychological tools), nor does it ask questions about physical and sexual abuse. Youth, ages 15-20, are not coerced into completing the survey. They are clearly told that they do not have to complete the survey if they do not want to and that they can skip any and all question(s) that they want to. To further protect the confidentiality of the subjects, NIH's Certificate of Confidentiality (CoC) policy automatically issues a CoC for any NIH-funded projects using identifiable, sensitive information. We inform youth that their answers will remain confidential and that the Certificate of Confidentiality protects them. Responses are kept completely confidential. Study IDs are assigned to the surveys and identifying information is kept in separate, secure encrypted electronic files at Emory University. No one has access to any of those files except for trained study personnel. Only the PI and research coordinator has access to the link list of study ID to participant name.

(2) The waiver or alteration will not adversely affect the rights and welfare of the subjects.

The letter sent to parents includes the information required for informed consent set forth in 45 CFR 46.116. The information that will be sent to parents explains the research purposes and duration; describes the procedures to be followed; lays out reasonable foreseeable risks; describes the extent to which confidential data identifying the subject will be maintained; explains whom to contact for answers to questions about the research; states that participation is voluntary and can be discontinued at any time; and indicates that refusal involves no penalty or loss of benefits. The parents can refuse participation for their child by calling [name] at Cherokee Nation Behavioral Health a toll-free number or by sending in a pre-addressed, stamped postcard. In addition, youth are given an assent form.

Youth participants also have the opportunity to easily refuse participation at any point in the survey process, including being able to skip any questions they choose. Hence these procedures meet national ethical and legal standards set forth in 45 CFR 46. The protocol has been carefully reviewed and approved by the IRB at the University of Florida and Cherokee Nation for the previous trial in the Cherokee Nation and is based on the protocol followed in our previous research over the past 25 years.

(3) The research could not practicably be carried out without the waiver or alteration.

A requirement to obtain written parental consent will significantly undermine the validity of the research study due to very low parental response rates among students most at risk for substance use, our key dependent variable (Dent et al., 1993; Ellickson & Hawes, 1989; Esbensen et al., 1999). In general, studies comparing various parental consent procedures suggest that requiring written consent can lead to biases on significant dependent variables that may adversely affect the generalizability of results of studies of adolescent drug use (Esbensen et al., 1999; Pokorny et al., 2001). It has been shown that requiring written parental consent threatens the scientific validity of research since only 28% to 43% of parents take the time to return signed consent forms, yet only about 3% of those actually withhold consent (Gottfredson, Jones & Gore, 1996). When requiring written consent, Ellickson and Hawes concluded that nonresponse was considerably more likely to signify latent consent than a deliberate refusal. In addition, researchers who have used active consent have reported unacceptably low response rates and underrepresentation of important groups, including racial/ethnic minority youth (Dent et al., 1993; Ellickson & Hawes, 1989; Esbensen et al., 1999). Therefore, if written parental consent was required in the proposed study, we would only be surveying less than half of the students who participated in the prevention program, with obvious bias in who completes the survey. In a study comparing parent consent procedures, Ellickson and Hawes concluded that carefully designed procedures that do not require signatures from parents can inform parents while avoiding the large nonresponse rates and sample bias associated with requiring written consent. We will send a series of personal letters (postcard, consent letter, postcard reminder) to each parent.

(4) Whenever appropriate, subjects will be provided with additional pertinent information after participation.

At the conclusion of this project, all parents and students will be sent a letter summarizing the aggregate results of the study. No personal identifying information will be provided, rather a summary of the overall study results will be provided so that families will be informed about study findings. An example of the study findings brochure from our previous study is included in this packet.

